Participants with CAC score ≥ 400	Vitamin K+D group	Placebo group	Group difference	
AU	Mean change from baseline (95 % CI)	Mean change from baseline (95 % CI)	Treatment effect (95 % CI)	P-value
Plaque volume and	d composition	1 (55 % 5.)	l	
Total plaque (mm³)				
Calcified plaque (mm³)				
Noncalcified plaque (mm³)				

Low-attenuation		
noncalcified		
plaque (<30 HU)		
(mm³)		
Plaque burden		
T		
Total plaque		
burden (%)		
Calcified plaque		
(%)		
Noncalcified		
plaque (%)		
Low-attenuation		
noncalcified		
plaque (<30 HU)		
(%)		

Figure 1. Enrolment and Randomization of Patients.

* Excluded due to known CVD, including MI, PCI and CABG procedure

[figure not shown]

Figure 2. CAC score progression according to treatment allocation.

CAC score at baseline, 12, and 24 months will be presented as line graph for the two treatment groups presenting mean with 95% confidence interval (as obtained from the linear mixed models applied for Table 3). Moreover it will be presented for the two subgroups (CAC score < 400 and ≥400 AU). (See mockup figure 2A below, 2B and 2C are similar)

[figure not shown]

Figure 3. Change in plaque volume from baseline to 24 months

Change in plaque volume (mm³) with the 4 groups (total, calcified, noncalcified, low-attenuation noncalcified plaque) from baseline to 24 months follow-up will be presented as a box plot to show difference between the treatment group and placebo group.

[figure not shown]
[figure not shown]

Figure 4. Forest plot of stratified analyses of the primary outcome

Coefficients with 95% confidence intervals from stratified analyses (as reported in Table 4) for differences in primary outcome (change of CAC score from baseline to 24 months) between treatment groups will be presented as a forest plot. (See mockup figure below.)

Planned analyses for secondary publication: Changes in volumetric bone mineral density in the lumbar spine and total hip

Exclusion criteria

Participants with use of prednisolone, anti-osteoporotic drugs, and patients with metabolic bone diseases (such as: prostate cancer, bone metastatic cancers, myelotomies, rheumatoid arthritis, primary hyperparathyroidism), patient with immobilization during observation will be excluded.

Outcomes

Primary outcome

- Co-primary outcome 1: change in BMD in spine from baseline to 24 month (numerical)
- Co-primary outcome 1: change in BMD in hip from baseline to 24 month (numerical)

Secondary outcomes

The secondary outcomes are as follows:

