Primary and secondary numerical outcomes will be analyzed by mixed effects linear regression. The mixed effects linear regression models will include a fixed effect for treatment, a fixed effect for time point (baseline and 24 months) and a fixed effects interaction between treatment and time point. As baseline measurements are obtained before randomization, treatment at baseline will be modelled as a separate common treatment category, constraining baseline measurements to no systematic treatment effect between the two treatment arms, as suggested in literature (6). All mixed effects models will include a random intercept for each included patient. Normality assumptions on residuals and random effects will be evaluated by normal quantile-quantile plots. In case deviations from normality assumptions are detected analyses will be repeated with nonparametric bootstrapping with 1,000 bootstrapping samples (handling individual patients as bootstrapping clusters, and treatment groups as bootstrapping strata).

Missing data will be excluded from analyses in Table 2 (but see sensitivity analyses below).

Table 2 might be split into multiple tables in the resulting manuscript to ease dissemination.

		Vitamin K +D	Placebo		
		group			
		Mean change	group Mean change	Treatment effect	P-value
		(95 % CI)	Mean change (95 % CI)	(95 % CI)	r-value
Primary outcomes		(33 % CI)	(33 /0 CI)	(33 /0 CI)	1
Volumetric BMD in	0 – 24 months				
spine	0 – 24 months				
Volumetric BMD in	0 – 24 months				
hip	0 – 24 months				
Secondary outcomes					
Volumetric bone minera	I density (mg/cm3)				
voidifietric borie miliera	ruensity (mg/cms)				
Trabeculært vBMD	0 – 24 months				
total hip					
Trabeculært vBMD	0 – 24 months				
femoral neck					
Trabeculært vBMD	0 – 24 months				
inter-trochanteric					
regions					
Trabeculært vBMD	0 – 24 months				
sub-trochancheric					
regions					
Cortical vBMD total	0 – 24 months				
hip					
Cortical vBMD	0 – 24 months				
femoral neck					
Cortical vBMD inter-	0 – 24 months				
trochanteric regions					
Cortical vBMD sub-	0 – 24 months				
trochancheric					
regions					
Bone geometry (cm2)		1			1
Trabecular area sub-	0 – 24 months				
trochancheric					
regions					
Trabecular area	0 – 24 months				
femoral neck					
Trabecular area	0 – 24 months				
inter-trochanteric					
regions					
Trabecular area sub-	0 – 24 months				
trochancheric					
regions					
Cortical area sub-	0 – 24 months				
trochancheric					
regions					

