Cortical area	0 – 24 months				
femoral neck					

Cortical area inter- trochanteric regions	0 – 24 months					
Cortical area sub-	0 – 24 months					
trochancheric						
regions						
Bone microstructure (cm)					
Cortical thickness	0 – 24 months					
sub-trochancheric						
regions						
Cortical thickness	0 – 24 months					
femoral neck						
Cortical thickness	0 – 24 months					
inter-trochanteric						
regions						
Cortical thickness	0 – 24 months					
sub-trochancheric						
regions						
Estimated bone strength						
CSMi (cm4)	0 – 24 months					
Section Modulus	0 – 24 months					
(cm3)						

Supplementary Table S1. Sensitivity analysis: Primary outcome with imputation

If more than 5% of observations are missing at 24 months for the main analysis of the primary outcomes reported in Table 2 the analysis will be repeated using multiple imputation (assuming missing at random) by linear regression with all baseline characteristics included in Table 1 as covariates generating 100 imputation sets. Results will be reported in a table structured as Table 2.

Supplementary Table S2. Main analyses adjusted for baseline characteristics

Main analysis as included in Table 2 will be repeated adjusted for D vitamin level and calcium intake at baseline as numerical covariates. The adjusted results will reported in a table structured as Table 2.

Supplementary Table S3. Mean and standard deviation of outcomes at baseline and 24 months

Mean and standard deviation (SD) for all outcomes stratified by treatment group will be reported at baseline and at 24 months.

	Baseline		24 months		
	Vitamin K +D Placebo group		Vitamin K +D	Placebo group	
	group		group		
	Mean (SD)	Mean (SD)	Mean (SD)	Mean (SD)	
Primary outcomes					
Volumetric BMD in					
spine					

Volumetric BMD in			
hip			
Secondary outcome	S		
Volumetric bone mi	neral density (mg/cm3	3)	
Trabeculært vBMD			
total hip			
Trabeculært vBMD			
femoral neck			
Trabeculært vBMD			
inter-trochanteric			
regions			
Trabeculært vBMD			
sub-trochancheric			
regions			
Cortical vBMD			
total hip			
Cortical vBMD			
femoral neck			
Cortical vBMD			
inter-trochanteric			
regions			
Cortical vBMD			
sub-trochancheric			
regions			
Bone geometry (cm2	2)		
Trabecular area			
sub-trochancheric			
regions			
Trabecular area			
femoral neck			
Trabecular area			
inter-trochanteric			
regions			
Trabecular area			
sub-trochancheric			
regions			
Cortical area sub-			
trochancheric			
regions			
Cortical area			

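### The BMD analysis adjusted for vitamin D and calcium intake (Supplementary Table S2) names no covariate-by-time term, so as written it captures only a small part of any effect of these covariates on BMD change

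*SAP*

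**What the plan says.** The co-primary outcomes of the BMD publication are changes over 24 months, for the spine "change in BMD in spine from baseline to 24 month (numerical" and likewise for the hip.

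The Table 2 model treats BMD at both visits as outcome. It has a treatment effect, "a fixed effect for time point (baseline and 24 months) and a fixed effects interaction between treatment and time point". The arms share one baseline mean: "treatment at baseline will be modelled as a separate common treatment category". The covariance is set by one term: "All mixed effects models will include a random intercept for each included patient".

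Supplementary Table S2 then runs that model again, "adjusted for D vitamin level and calcium intake at baseline as numerical covariates". On reporting it says: "The adjusted results will reported in a table structured as Table 2". The result is thus again mean change per arm and a treatment effect on change. The Table 2 text spells out its treatment-by-time interaction. The S2 text names no interaction for the two covariates, and nothing else in the BMD section adds one.

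**The concern.** A baseline covariate takes the same value on both rows of a patient's data. Entered as a main effect, it adds the same amount to baseline BMD and to 24-month BMD, and that amount cancels from the within-patient change. An effect of vitamin D or calcium intake on bone loss or gain over 24 months has almost nowhere to go in such a model.

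S2 covers every Table 2 outcome, both co-primaries included, and the active arm receives vitamin K plus D, so readers will look at baseline vitamin D. If S2 nearly reproduces Table 2, it may be taken to show that the result does not depend on vitamin D or calcium status, although the model had little capacity to show otherwise. Any precision that the covariates could bring is lost as well.

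**Working it through.** The SAP gives no figure for S2, so there is none to reproduce. Model structure, estimand and 1:1 allocation come from the SAP; every number below is an assumption or follows from one.

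**Algebra.** Let D0 and D1 be the arm differences in mean BMD at baseline and 24 months, ΔX the arm difference in a covariate, and ρ the correlation implied by the random intercept. Let b0 and b1 be the covariate's slopes on BMD at the two visits, and c = b1 − b0 its effect on change. With two visits and a common baseline mean, the estimated treatment effect is:

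- no covariate: D1 − ρD0
- covariate main effect: D1 − ρD0 − (1 − ρ)·b·ΔX, with one slope b ≈ b0 + c/2 shared by both visits
- covariate × time: D1 − ρD0 − (b1 − ρb0)·ΔX

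(ρ differs slightly between fits; one symbol is used here.) The shift due to imbalance is therefore:

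- unadjusted: [(1 − ρ)b0 + c]·ΔX
- removed by main effects: (1 − ρ)(b0 + c/2)·ΔX
- left after main effects: c·(1 + ρ)/2·ΔX

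Main effects remove the part due to BMD level but leave (1 + ρ)/2 of the part due to change: 90% at ρ = 0.80 and 99% at ρ = 0.98.

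**Scenario A: ΔX = 0.2 SD, c = 0.3 SD of baseline BMD, 300 patients.**

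- With b0 = 0 the share removed is (1 − ρ′)/2. Omitting the interaction lowers the fitted correlation, so 1 − ρ′ = (1 − ρ + c²/2)/(1 + c²/4). At ρ = 0.80 this is (0.20 + 0.045)/1.0225 = 0.240, so 12% is removed. At ρ = 0.98 it is (0.02 + 0.045)/1.0225 = 0.064, so 3%. Simulation with REML fits gave 12%, 7%, 5% and 3% at ρ = 0.80, 0.90, 0.95 and 0.98.
- With a covariate also related to baseline BMD, simulation gave 26%, 17%, 11% and 8%. At the most favourable corner (b0 = 0.4, ρ = 0.80) the simple formula gives 0.20 × 0.55 / (0.20 × 0.4 + 0.3) = 0.11/0.38 = 29%, slightly above the simulated range.
- At ρ = 0.95 the simulated shift fell from 0.066 to 0.058 SD. With covariate × time, less than 0.004 remained.
- At ρ = 0.95 the standard error was almost unchanged by main effects but fell from 0.049 to 0.036 with covariate × time.

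Scenario A assumes a strong covariate. At ρ = 0.95 the residual variance of change is 2 × 0.05 = 0.10, so c = 0.3 explains 0.09/(0.09 + 0.10) = 47% of the variance of change.

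**Scenario B: two covariates together explain 5% of baseline BMD variance and 20% of change variance, 300 patients.** In SDs of change per unit of summed imbalance:

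| ρ | Main effects | Covariate × time | Share captured |
|---|---|---|---|
| 0.80 | 0.070 | 0.313 | 22% |
| 0.90 | 0.047 | 0.318 | 15% |
| 0.95 | 0.031 | 0.313 | 10% |
| 0.98 | 0.018 | 0.315 | 6% |

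Check at ρ = 0.95: b0 = √0.025 = 0.158; SD of change = √0.10 = 0.316; b1 = 0.95 × 0.158 + 0.316 × √0.10 = 0.250; mean slope 0.204. Main effects: 0.05 × 0.204/0.316 = 0.032. Full: (0.250 − 0.150)/0.316 = 0.316. Both agree with the simulation.

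The standard error at ρ = 0.95 goes from 0.1118 to 0.1117 with main effects and to 0.1020 with covariate × time, about 9% lower. If the covariates explain 5% of each variance, the captured share is 37%, 27%, 18% and 11% for the four values of ρ, and covariate × time lowers the standard error by only 1–2%.

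**The case against.** **The SAP does not exclude interactions.** The word numerical fixes the scale of the covariates, not how they enter. The coronary publication's adjusted table (its Supplementary Table S1) labels its coefficients as relating to change, so the authors may think of adjustment that way. This stands as a limit: the point rests on the ordinary reading of the text. It does not settle the matter, because that table belongs to another publication and the two readings give materially different adjustments.

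**S2 may be meant for imbalance in BMD level.** The SAP gives no rationale, so one cannot say that an effect on change is the reason for S2. If a covariate acts equally on both visits (c = 0), main effects remove the whole shift, though that shift is small. With b0 = 0.2 and c = 0.1 they remove 0.20 × 0.25 / (0.20 × 0.2 + 0.1) = 36% at ρ = 0.80 and 0.005/0.104 = 5% at ρ = 0.98. The share thus depends on quantities that the SAP does not give.

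**The shift is conditional on chance imbalance.** With 150 per arm the standard error of a covariate difference is √(2/150) = 0.115 SD, so an imbalance of 0.2 SD or more (z = 1.73) arises in about 8% of trials for a given covariate. This stands. S2 is supplementary, and no decision rule depends on it.

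**Stronger readings to avoid.** A reader might infer that S2 tests nothing, or that its estimate copies Table 2 whatever the imbalance. Neither follows: the shift is proportional to the imbalance and is reduced, not zero. Nor does it follow that Table 2 is biased, since allocation is randomised.

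**Conclusion.** The point holds as a minor one. Read as written, S2 adjusts well for a covariate's relation to BMD level but leaves (1 + ρ)/2 of any effect on BMD change, which is the reported outcome. Under the assumed inputs main effects remove about 3–26% of the imbalance-related shift, somewhat more if ρ is near 0.80 and the covariate relates mainly to level. Almost no precision is gained.

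The conclusion depends on reading the covariates as main effects and on ρ being high; it is strongest at 0.90 and above. The SAP states neither ρ nor the covariate effects. What is at stake is the interpretation of S2: closeness to Table 2 would be weak evidence of robustness to vitamin D and calcium status. The Table 2 estimate is not called into question.

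**What to change.** State in Supplementary Table S2 that baseline vitamin D and baseline calcium intake each enter the Table 2 model with a main effect and an interaction with time point. This costs one phrase in the SAP and two extra parameters per model, with no new data.

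An alternative is ANCOVA of 24-month BMD on baseline BMD, treatment and both covariates. In the simulations it gave nearly the same adjustment. It is not identical to the planned model: it uses only patients with both measurements and estimates the baseline slope freely, whereas the random-intercept model can use patients with one measurement and assumes equal variances at the two visits.
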